Balance Recovery Training for Fall Prevention in Retirement Communities

NCT02551666

October 13, 2015

STATISTICAL ANALYSIS PLAN

Baseline-post intervention changes in clinical and reactive balance measures were compared between RBT and Tai Chi groups using a mixed model (SAS PROC MIXED procedure, SAS Institute Inc., Cary NC) that accounted for fixed and random effects, and within-participant correlation. For the clinical tests, fixed effects of intervention (RBT or Tai Chi), time (one week, one month, three months, or six months post-intervention), and intervention*time were included, as well as covariates of baseline (pre-intervention) performance, age, gender, and baseline reactive balance rating score. For the reactive balance measures, fixed effects of intervention, time, speed, and all two-factor interactions were included, along with the same covariates noted above. Hierarchical models were used in analyzing reactive balance measures to account for the two levels of repeated measures (time and speed) and the two replications of each time-speed combination. *A priori* simple effects investigated differences between intervention groups at each time point to address our hypotheses, and the Tukey-Kramer method was used to adjust for Type I error rate, with a significance level of $p \leq .05$. Differences in categorical variables between groups were evaluated using Fisher's Exact Test.

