Balance Recovery Training for Fall Prevention in Retirement Communities

NCT02551666

October 13, 2015

STUDY PROTOCOL

Objective

The objective of this study was to compare the efficacy of RBT versus Tai Chi performed at, and among residents of, older adult senior housing. This RBT is a form of task-specific, perturbation-based balance training involving trip-like perturbations on a modified treadmill (1, 2). Based on evidence of fall risk reduction among older adults (3) and wide implementation, Tai Chi was chosen as an active control training exercise. Outcome measures included reactive balance tests involving trip-like perturbations on the modified treadmill, and standard clinical tests of balance and mobility. We tested two hypotheses, both of which were motivated by the principle of training specificity. We hypothesized that participants randomized to RBT would show better performance on reactive balance tests compared to participants randomized to Tai Chi. We also hypothesized that participants randomized to Tai Chi would show better performance on clinical tests of balance and mobility compared to participants randomized to RBT.

Design

A two-group pretest-posttest design was used. Participants were allocated to RBT or Tai Chi using a computer-based algorithm to minimize differences in key confounders including age (70-79 or 80 and over), gender (male or female), and baseline reactive balance rating (RBR) score (0-12). The pretest was conducted approximately one week prior to starting the assigned intervention. Repeated posttests were conducted one week, one month, three months, and six months after completing the intervention. In addition, real-world falls were tracked for the six months after completing the intervention.

Methods

Pretests and posttests were identical and included a battery of balance tests. The battery of balance tests included six standard clinical tests of balance and mobility, and a reactive balance test. All tests were performed by an investigator who was blinded to participants' group assignment.

Clinical tests: Six fall-risk relevant tests of balance, mobility, and balance confidence were included along with their standard scoring: timed-up-and-go test (TUG) (4), unipedal stance time (5), maximum step length (6), Berg Balance Scale (7), Performance-Oriented Mobility Assessment (POMA) (8), and Activities-specific Balance Confidence Scale (ABC) (9).

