Reactive balance test: Participants stood on a stationary modified treadmill (Freemotion 800, Freemotion Fitness, Logan, UT), and reactive balance was assessed in response to a sudden treadmill belt posterior acceleration (~ 40 msec). A slender, rectangular foam block (4×4 cm cross section) was positioned approximately 3-7 cm in front of the toes to elicit a step over an obstacle, similar to that needed after a trip. Participants wore a fall protection harness, supported by an overhead gantry, to prevent knee or hand contact with the treadmill in the event of an unsuccessful attempt to recover balance. Participants were instructed to, upon treadmill movement, step over the obstacle, prevent a fall into the harness, and re-establish stable walking. Two perturbations were performed at each of three speeds (0.8 mph, 1.6 mph, and 2.4 mph) to provide three levels of difficulty (along with two trials at 0.8 mph in the reverse belt direction to reduce anticipation, but these were not included in characterizing reactive balance).

Interventions: Both RBT and Tai Chi interventions involved twelve 30-minute sessions, scheduled three times per week for four weeks. Participants were required to complete at least nine sessions (75% of the total 12) to be considered to be adherent to the protocol; mean RBT and Tai Chi

attendance was 91% and 94%, respectively. Each RBT session involved one participant at a time, and up to 40 treadmill perturbations with rest breaks every 10 perturbations. Perturbations were similar to those during reactive balance tests, with speed and direction (backward or forward belt movement) pseudorandomized to minimize anticipation, and speeds individualized to each participant's capabilities. Each Tai Chi session was led by an instructor with experience in leading community-based Tai Chi for older adults, used 12 unique sequences from the Yang Short Form, and was conducted in groups of a mean size of 5.3 participants. All testing and intervention sessions were performed on-site at the senior housing facilities.

Falls assessment: The number of all-cause falls and trip-induced falls outside of testing and training were recorded over the six months after the intervention (from week 5 to week 28). Such falls were quantified through telephone calls made every two weeks to each participant. A fall was defined as unintentionally coming to rest on the ground or lower level, not caused by loss of consciousness or overwhelming hazard (10).

REFERENCES

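### Does leaving the reactive-balance response unnamed undermine the test of hypothesis 1?

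*SAP*

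**What the plan says.** The Protocol (Objective) sets two hypotheses: RBT does better on reactive balance, and Tai Chi does better on clinical tests. On the first it says: "Outcome measures included reactive balance tests involving trip-like perturbations on the modified treadmill". The Methods section on the reactive balance test describes the apparatus and the task. It says that "reactive balance was assessed in response to a sudden treadmill belt posterior acceleration", with two trials at each of three speeds, but it does not say what is recorded from a trial. The six clinical tests are listed by name with their usual scoring.

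The one reactive score named is in the Protocol's Design section, as an allocation factor: "baseline reactive balance rating (RBR) score (0-12" is its label and range. In the SAP it returns as a covariate: "as well as covariates of baseline (pre-intervention) performance, age, gender, and baseline reactive balance rating score".

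For the reactive outcomes the SAP states: "For the reactive balance measures, fixed effects of intervention, time, speed, and all two-factor interactions were included". It adds the same covariates and a hierarchical structure for "the two replications of each time-speed combination". On the contrasts it says that *a priori* "simple effects investigated differences between intervention groups at each time point to address our hypotheses", with Tukey-Kramer adjustment at the .05 level. Both documents carry the date "October 13, 2015".

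**The concern.** Hypothesis 1 is one of the trial's two claims, and its response is called only *measures*, in the plural. Two analysts could take different quantities from the same trials (a rating, a step characteristic, a success indicator), reach different answers, and each call the contrasts *a priori*. Tukey-Kramer works within one fitted model and gives no protection against choosing among several.

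The obvious candidate, the RBR, does not seem to fit. It is given as a single 0-12 score, while the model has speed and replication in it. Its baseline would also seem to enter twice, once as baseline performance and once as baseline RBR.

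Nor can the date be used to show that the response was fixed in advance. The Protocol under that date cites a 2017 paper and reports attendance and class size as achieved. If the response had been picked after the data were seen, the evidence for hypothesis 1 would be weaker than it looks.

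**Working it through.** The documents state no figure on this point, so there is none to reproduce. The check has four steps.

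**1. What is named.** Reactive responses named: 0. Clinical tests named: 6. The omission is confirmed.

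**2. Does the model structure rule out the RBR?** Inputs: 3 speeds and 2 trials per speed (Protocol, Reactive balance test); 4 posttests (Protocol, Design; SAP).

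- Values the model uses per visit: 3 × 2 = 6. Over four posttests: 6 × 4 = 24.
- Values from one RBR total per visit: 1 × 4 = 4, with no speed or replicate level.

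A visit total therefore cannot be the response. But 12 points over 6 trials is 12/6 = 2 points per trial. A 0-2 rating of each trial that sums to 0-12 would give exactly the 24 values required. This is an inference from the arithmetic; neither document states it. On that reading, baseline performance at trial or speed level is a different covariate from the baseline total. Having the total in the model is also natural, because allocation was balanced on it. If the two baseline terms were identical, the second would be redundant and the adjusted group contrasts would not change.

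**3. How large is the multiplicity?** Let *k* be the number of reactive measures. It is not given, so it is an assumption here. Suppose .05 holds within each measure. For independent measures the chance of at least one false difference is 1 − 0.95^k. The last column counts only false differences favouring RBT, 1 − 0.975^k, since hypothesis 1 is directional. It assumes two-sided tests; the SAP does not state sidedness.

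| k | Either direction, independent | Either direction, correlation 0.5 | Favouring RBT, independent |
|---|---|---|---|
| 1 | 5.0% | 5.0% | 2.5% |
| 2 | 9.75% | 9.1% | 4.9% |
| 3 | 14.3% | 12.5% | 7.3% |
| 5 | 22.6% | 18.3% | 11.9% |

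With perfect correlation, the either-direction rate is 5% for every *k*. The plural does not settle *k*. The Protocol uses both *tests* and *test* for the same reactive procedure, and the SAP speaks of repeated measures when it means time and speed. One variable recorded over speeds, visits and replicates fits the wording.

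The same argument would apply to hypothesis 2, where the count is documented: six tests, none designated, and 1 − 0.95^6 = 26.5% if independent. It is therefore not specific to the unnamed reactive response.

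**4. What does the date show?** The 2017 citation, the attendance of 91% and 94% and the mean class size of 5.3 are all in the Protocol. They show that some of the Protocol text was written after the printed date. The SAP contains nothing of that kind. It is in the past tense, but that does not date the choice of response. In the SAP, *a priori* qualifies the simple effects, meaning the group contrasts at each time point. It makes no claim about when an outcome was selected.

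**The case for a change.** The strongest case for the concern is that a reader cannot tell from either document what was analysed for hypothesis 1. A per-trial RBR is only a guess from 12/6 = 2. If there is more than one measure, no rule says which decides. Nothing marks removed text at these places, so redaction does not explain the gap, and the six clinical tests show that the authors could name outcomes when they chose to.

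The omission stands: response, scoring and unit are not written down, and a list would help the reader. The step from there to a faulty analysis does not stand. The model already narrows the field, because the response has to be a quantity obtained on each of the six scored trials, with a baseline counterpart. That is detail the analysts would have had to hand. The error rates need a *k* that the documents do not supply. The date argument cannot reach the SAP, and nothing suggests that the response was chosen after the results were known.

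**Conclusion.** No change to the plan follows. The gap is in description: the reactive response is left to be read from the test procedure and the structure of the model. Supplying it would record what was analysed without altering a model, a contrast or an error rate that the SAP states.

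The size is indeterminate. There is no inflation if *k* = 1, and at *k* = 2 the either-direction rate lies between 5% (perfect correlation) and 9.75% (independence). Higher figures need a larger *k*, for which the documents give no support. Designating one deciding measure, or adjusting across several, would be a remedy for a multiplicity that has not been shown to exist on the reactive side.

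The conclusion rests on two readings: that *measures* can mean one variable observed repeatedly, and that a per-trial score compatible with the model exists. Both fit the text, and neither is proved by it. The Protocol's later material is worth knowing when its date is cited, but it says nothing about when the SAP's reactive response was chosen.

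### Tukey-Kramer is named without a family of means, and neither obvious family matches the four planned RBT-versus-Tai-Chi contrasts per outcome

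*SAP*

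**What the plan says.** The Protocol (Objective) sets two directional hypotheses: that "participants randomized to RBT would show better performance on reactive balance tests compared to participants randomized to Tai Chi", and that "participants randomized to Tai Chi would show better performance on clinical tests of balance and mobility". The SAP tests them through a priori contrasts: "simple effects investigated differences between intervention groups at each time point to address our hypotheses". The time factor has four levels, "time (one week, one month, three months, or six months post-intervention". Baseline enters as a covariate, not as a fifth level. Two arms and four times give four planned contrasts per outcome.

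In the same sentence the SAP adds that "the Tukey-Kramer method was used to adjust for Type I error rate", at a 0.05 level. It does not say which means or comparisons this covers, and the Protocol says nothing on multiplicity. For the reactive measures, "fixed effects of intervention, time, speed, and all two-factor interactions were included", so that model also contains speed.

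**The concern.** Tukey-Kramer protects the full set of pairwise differences among k means. Four between-arm differences, one at each time, are not the full set of pairs of any family the SAP suggests. There are two obvious readings.

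- **Two arms within a time point (k = 2).** There is one pair, so the adjusted p-value equals the unadjusted one. Nothing protects the four time points.
- **Eight intervention-by-time cells (k = 8).** There are 28 pairs, of which 24 answer no stated hypothesis. Error is controlled, but more strictly than four contrasts require.

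The contrasts affected carry both hypotheses. A reader who sees an unadjusted p of 0.01 at one time point cannot tell whether the plan counts it as significant: it does under k = 2 and does not under k = 8.

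**Working it through.** **Inputs.** From the SAP: level 0.05, two arms, four times, Tukey-Kramer. From the Protocol (Methods): six clinical tests. The documents give no sample size, degrees of freedom (df), correlations or power target, so there is no planned figure to reproduce. Assumed: df from 30 to infinite, equal correlation 0-0.9 among the four contrasts of an outcome, and 80% or 90% unadjusted power for illustration. Tests are taken as two-sided.

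**1. Size of the family.** Cells: 2 × 4 = 8. Pairs: 8 × 7 / 2 = 28. Planned: 4. Unplanned: 28 − 4 = 24. This holds for the clinical tests, and for the reactive measures averaged over speed.

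**2. Threshold per contrast.** The critical t is q(0.95; k, df)/√2, where q is the studentized range quantile.

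- k = 2, infinite df: 2.772/√2 = 1.960, so the threshold is 0.05. It is 0.05 at every df.
- k = 8, infinite df: 4.286/√2 = 3.031, threshold 0.00244; 0.05/0.00244 = 20.5.
- k = 8, df = 60: threshold 0.00262, ratio 19.1.
- k = 8, df = 30: critical t 3.25, threshold 0.00282, ratio 17.7.
- Bonferroni over four: 0.05/4 = 0.0125, critical value 2.498 at infinite df.

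The critical value that gives exactly 5% over four contrasts is 2.49, 2.44, 2.32 and 2.24 at correlations 0, 0.5, 0.8 and 0.9. Both Tukey-Kramer values, 1.96 and 3.03, lie outside that range.

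**3. Chance of at least one false positive over the four contrasts.** With independence and k = 2 it is 1 − 0.95⁴ = 18.5%. For other correlations, 1,000,000 simulated sets of four equally correlated normal contrasts give:

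| Correlation | k = 2, two-sided | k = 2, hypothesised direction | k = 8, two-sided | Holm or Bonferroni over four, two-sided |
|---|---|---|---|---|
| 0 | 18.6% | 9.6% | 0.97% | 4.9% |
| 0.5 | 15.6% | 7.8% | 0.90% | 4.3% |
| 0.8 | 11.4% | 5.7% | 0.67% | 3.2% |
| 0.9 | 9.4% | 4.7% | 0.56% | 2.6% |

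At df = 30 and correlations 0, 0.5 and 0.9, the two-sided values are 18.1%, 15.2% and 9.2% for k = 2; 1.08%, 0.99% and 0.61% for k = 8; and 4.8%, 4.2% and 2.5% for Holm. Holm and Bonferroni share one column because, with no true difference, Holm makes a first rejection exactly when Bonferroni does.

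**4. Power.** A contrast with 80% unadjusted power has a standardised effect of 1.960 + 0.842 = 2.802 at infinite df.

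- Bonferroni over four: Φ(2.802 − 2.498) = 61.9% (59.7% at df = 30).
- k = 8: Φ(2.802 − 3.031) = 40.9% (38.0% at df = 30).
- Loss due to the 24 unplanned pairs: 61.9 − 40.9 = 21.0 points.

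With 90% unadjusted power the ranges are 75-77% and 55-58%. Holm at infinite df, for effects with 80% unadjusted power, gives 62% if only one time point has an effect, and 69-73% on average if all four do.

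**5. Across the six clinical tests.** 6 × 4 = 24 contrasts. With no true difference, between-test correlation 0-0.7 and between-time correlation 0.3-0.9 (200,000 draws), the chance of at least one false positive is 28-68% with k = 2, 2-6% with k = 8, and 9-25% with Holm within each test. If all 24 were independent, the Holm figure would be 1 − (1 − 0.0125)²⁴ = 26%.

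**The case against.** The strongest reply is that the SAP says an adjustment was made, so k = 8 is the natural reading, and under k = 8 no false-positive rate is exceeded. What remains is conservatism, which is an efficiency choice. Most of the illustrated power loss is not even disputed: if the reading is k = 8, about half of the fall from 80% is the price of any Bonferroni-type adjustment over four. This stands in part. Inflation cannot be asserted, and only the gap of about 21 points is charged to the unplanned pairs.

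The sentence could also mean that Tukey-Kramer was applied to other comparisons, such as those between times or speeds. The four planned contrasts would then be unadjusted, which has the same consequence as k = 2. It widens the ambiguity.

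The 19% figure needs zero correlation between contrasts on the same people, which is unlikely. At 0.5-0.9 the range is 16% down to 9%. In the hypothesised direction it falls just below 5% at 0.9. That is a fair limit on the size.

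A 5% family over four times is also a choice, since the SAP ties its 0.05 to no stated family and names no primary time point. But the SAP offers its adjustment in the same sentence as these contrasts, so a family built from them is the closest to its stated aim.

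Finally, multiplicity across the six tests is a separate question. It matters here only because replacing k = 8 by Holm weakens the incidental protection across tests, and that has to be disclosed.

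**Conclusion.** The point holds. The SAP leaves the threshold for every hypothesis-bearing contrast open by a factor of about 18 to 20 (0.05 against 0.0024-0.0028), and neither reading targets 5% over the four contrasts. Under k = 2 there is no adjustment. Under k = 8 error is controlled at 0.6-1.1% per outcome, with power spent on pairs that no hypothesis uses. Naming the family would remove the ambiguity but not the mismatch.

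The direction of these conclusions does not change over the assumed df and correlations, with one exception: the error in the hypothesised direction under k = 2 dips just under 5% at correlation 0.9. The power figures are illustrative, because the documents state no power target. This should be fixed, but it does not show that any result is invalid.

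**What to change.** 1. State which means the Tukey-Kramer adjustment was applied to.
2. Define the family as the four planned group contrasts per outcome, and name Holm as its method.
   - If k = 2 was used, or if outcome data have not been analysed, make Holm the main adjustment.
   - If k = 8 was used and outcome data have been seen, keep Tukey-Kramer as the main result and report Holm as a labelled sensitivity analysis. This guards against loosening the criterion after the fact. It is a live possibility: the SAP is in the past tense ("Baseline-post intervention changes in clinical and reactive balance measures were compared between RBT and Tai Chi groups"), and the Protocol (Interventions) already reports conduct ("attendance was 91% and 94%, respectively").
3. State plainly that p-values are not adjusted across the six clinical tests, and that with Holm within each test the two-sided error over the 24 contrasts is about 9-25%.

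**Cost.** SAP wording and a re-run of the group contrasts; no new data.

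- Against k = 2, some isolated p-values between 0.0125 and 0.05 lose significance, and error over the 24 clinical contrasts falls from about 28-68% to 9-25%.
- Against k = 8, where Holm is the main method, p-values from about 0.0024-0.0028 up to 0.0125 become significant. Values up to 0.05 can follow by step-down when the other contrasts are also significant. Error over the 24 contrasts rises from about 2-6% to 9-25%.
- Where Holm is only the sensitivity analysis, the main result does not change.
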